8.0 Study Endpoints

Primary Outcomes – Aim 2

Feasibility. Intervention feasibility will be evaluated by recruitment and retention in the RCT. We will record recruitment and enrollment statistics at every step (e.g., number of clicks on online ads, number who complete the screener, number of eligible participants, number randomized). Retention rates will be computed for each assessment period. An 80% 9-month retention rate will be used to indicate a feasible intervention.

Acceptability. Intervention acceptability will be assessed at the end of Phases 1 and 2 with an adapted version of a scale used in G2G³⁸ and KIU! (an online HIV prevention intervention; R34MH079714, [name] PI).⁴⁹ The scale includes both open- (“What did you like about the program? What could be improved?”) and closed-ended questions (e.g., “I would recommend a program like this to my friends” 1=strongly disagree to 5=strongly agree). Average scores ≥ 4 will be used to indicate an acceptable intervention.

Vaccination Status. A final confirmatory assessment of HPV vaccination status will be conducted at the 9-month follow-up. Participants will be asked whether they received any doses of HPV vaccine (yes/no) since baseline and if yes, the number of doses and where they were received. Vaccination status will be confirmed by consulting the Illinois Comprehensive Automated Immunization Registry (I-CARE). Pharmacies in Illinois are required to report all vaccinations to the registry,⁵⁰ thus any HPV vaccines administered at a local pharmacy over the trial will be documented in I-CARE. Medical chart data will be sought from those participants who report receiving any doses from their primary care physician over the 9-month trial and those doses are not found in I-CARE. Medical chart data will only be sought for those participants who sign the medical release form (see supporting documents).

Vaccination status will be checked in I-CARE at the beginning and end of the trial. Please see supporting documents and below for additional detail.

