Overview. The primary goal of Aim 2 is to pilot test the intervention to establish feasibility, acceptability, and preliminary efficacy. Young MSM in the Chicago metro area will be recruited primarily online as well as from Howard Brown Health Center, and randomly assigned to the treatment or control condition. The intervention will be divided into two phases: During Phase 1 (weeks 1 through 3) participants will receive about 10 messages per day (similar to G2G). During Phase 2 (weeks 4 through 36) message frequency will decrease to monthly messages. The precise number of messages sent per day and delivery schedule may be altered based on feedback from participants in Aim 1. To give participants sufficient time to get vaccinated and because HPV vaccination is currently achieved with 3 doses administered over a 6-month period, participants will be followed for 9 months. Participants will complete assessments at baseline, immediately after Phase 1, and at the end of the 9-month trial (in order to observe all doses). Upon study completion, vaccination status will be verified by participants' medical records and the Illinois Immunization Registry, which tracks pharmacy-delivered vaccines.

Pilot RCT. Participants will be randomized 1:1 to the treatment or control condition using the REDCap (Research Electronic Data Capture) randomization module. Intervention content will be delivered in two phases over a 36-week period. During Phase 1 (weeks 1 through 3), participants will receive about 10 messages daily. During Phase 2 (weeks 4 through 36), message frequency will decrease to monthly messages. To match for attention, message frequency will be equal across the treatment and control conditions. During Phase 2, participants will receive up to three "pop-up" surveys where they will be able to inform us if/when they receive a/each dose of HPV vaccine so messages can be appropriately tailored (e.g., switch from promoting initiation to completion of the 3-dose series). Participants with a primary care provider will be instructed to contact their provider about receiving the vaccine. If their provider does not carry the vaccine, participants will be directed to seek the vaccine at a local pharmacy (e.g., Walgreens, CVS). Uninsured and underinsured participants will be directed to HBHC, a FQHC that provides care on a sliding fee scale.

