Data for the in-depth interviews will be collected in person or by phone. Interviews will take place in the privacy of the PI's ([name]) office and will last approximately 45-60 minutes. Participants will be able to skip any questions they are not comfortable answering.

Surveys will include sensitive questions such as questions about sexual behavior. The benefits to collecting data online include increased self-disclosure compared to interviewer-based data collection; convenience for the participant, as he can decide when to complete it; and increased safety, as he can decide when and where it is best to answer these questions. Participants will also be able to skip any questions that make them uncomfortable.

We are sensitive to how the survey experience can affect the validity of the data. All online surveys will be as brief as possible and configured for easy completion on multiple platforms (e.g., cell phone, tablet, laptop). Based on previous research, we estimate that the Step 1 online survey will take approximately 10-15 minutes, the baseline survey will take approximately 15-20 minutes, the immediate post-test survey (end of Phase 1) will take approximately 25-30 minutes, and the end of trial survey will take about 15-20 minutes. The shorter version of the end of trial survey offered to participants who are difficult to reach and out of window will take about 5 minutes. Pop-up surveys (during Phase 2) will take less than one minute to complete.

HPV vaccination status will be verified via the Illinois Comprehensive Automated Immunization Registry (I-CARE) and participants' medical chart. Vaccination status will be confirmed in I-CARE for all RCT participants both before participants begin receiving messages and at the end of the 9-month trial. Pharmacies in the state of Illinois are required to report all vaccinations to the registry,⁵⁷ thus any HPV vaccines administered to participants at a local pharmacy over the course of the 9-month trial will be documented in I-CARE.

Additionally, medical chart data will be sought from those participants who report receiving any doses of HPV vaccine from their primary care physician over the 9-month

PROTOCOL TITLE: txt2protect

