trial and those doses are not found in I-CARE. The project coordinator will contact these participants at the end of the trial and ask them to complete the medical release form (see supporting documents). Upon receipt of the signed form, the project coordinator will contact the participant's primary care doctor to verify the number and timing of any HPV vaccine doses that were received during the trial. Medical chart data will only be sought for those participants who sign the medical release form.

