11.0 Data and Specimen Management

Analysis Strategy

Intervention feasibility will be computed as outlined above and summarized in a CONSORT map. Acceptability of the intervention will be assessed with descriptive statistics for the closed-ended items and with the same qualitative approach used for the online FG data for the open-ended items. Intervention efficacy will be assessed using an intent-to-treat approach. T-tests and chi-square analyses will be used to compare baseline characteristics of participants in the treatment vs. control condition. Separate chi-square analyses will be conducted for HPV vaccine initiation (receipt of ≥ 1 dose) and completion (receipt of 3 doses) to assess effects of treatment. Secondary analyses will examine potential differences in IMB constructs at the end of Phase 1 by treatment arm and assess whether they mediate effects of t2p on vaccine uptake. Following [name],³⁴ we will also conduct a detailed analysis of barriers to vaccine uptake among participants who did not get vaccinated over the course of the study to inform additional modifications for the large-scale trial.

Power Analysis

Based on previous studies,^{14, 41, 43, 54} we hypothesize that 18-21% of treatment arm participants will receive their 1st dose of HPV vaccine, compared to 6-8% of control arm participants. The comparison of outcomes between arms, with two-sided alpha = 0.05, will have $> 80\%$ power for all scenarios with N=192 per condition. Based on previous

PROTOCOL TITLE: txt2protect

studies with similar samples (G2G, Keep It Up! [KIU!])^{38, 49} and retention rates as high as 85-95% with follow-ups as long as one year, we anticipate an attrition rate of 5-20%. Using the most conservative estimate (20%) we will enroll 230 participants per arm to account for attrition.

Steps to Maintain Data Security and Confidentiality

Participant privacy and data will be carefully protected. Online surveys will be conducted online using a secure web-based application (REDCap).

To maintain privacy in the online focus groups, all participants will be asked to use pseudonyms rather than their real names, and to refrain from mentioning others by name. This will help to ensure openness. If any personal information is inadvertently disclosed, names or other identifying information will be redacted from the focus group transcripts.

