On the eligibility screener, participants will be asked whether they have been vaccinated against HPV. It is possible that some participants will not know their status. Although Step 1 will involve participants who have and have not been vaccinated against HPV, enrollment for Steps 3 and 5 as well as the pilot RCT will be limited to unvaccinated participants, thus it will be important to confirm vaccination status before participants are enrolled in the study. Before enrollment begins, we will consult the Illinois Immunization Registry (I-CARE) to assess HPV vaccination status for all participants who have provided consent and meet eligibility criteria for the study.

Vaccination status will be confirmed in I-CARE for all RCT participants both before participants begin receiving messages and at the end of the 9-month trial.

Additionally, medical chart data will be sought from those participants who report receiving any doses of HPV vaccine from their primary care physician over the 9-month trial and those doses are not found in I-CARE. The project coordinator will contact these participants at the end of the trial and ask them to complete the medical release form (see supporting documents). Upon receipt of the signed form, the project coordinator will contact the participant's primary care doctor to verify number and timing of any HPV vaccine doses that were received during the trial. Medical chart data will only be sought for those participants who sign the medical release form.

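### The medical release is requested only at the end of the trial, so a physician-given dose that is missing from I-CARE and was reported earlier cannot be chart-verified if the man is unreachable by month 9

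*Combined protocol and SAP*

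**What the plan says.** Verification has two sources.

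- **Registry.** Section 9.0 (Sources of Materials) states: "Vaccination status will be confirmed in I-CARE for all RCT participants", before messages begin and again at the end of the 9 months. Because pharmacies must report, "any HPV vaccines administered to participants at a local pharmacy over the course of the 9-month trial will be documented in I-CARE".
- **Chart.** For doses not found in the registry, "medical chart data will be sought from those participants who report receiving any doses of HPV vaccine from their primary care physician". Section 9.0 gives the timing of the release: the coordinator will "contact these participants at the end of the trial and ask them to complete the medical release form". Section 25.0 repeats it: "The project coordinator will contact these participants at the end of the trial and ask them to complete the medical release form". Section 8.0 adds the condition: "Medical chart data will only be sought for those participants who sign the medical release form". No earlier request is described.

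Reports of doses can arrive well before month 9. Section 9.0 (Pilot RCT) provides up to three Phase 2 pop-up surveys in which "they will be able to inform us if/when they receive a/each dose of HPV vaccine". The same section sends men who have a primary care provider to that provider first, with a pharmacy as the alternative when the provider does not stock the vaccine. On loss to follow-up, section 11.0 says "we anticipate an attrition rate of 5-20" per cent.

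**The concern.** The chart is the back-up for physician-given doses that do not reach I-CARE. The plan claims full registry capture only for pharmacies, yet it makes the physician the first place to go. The permission that opens the chart is sought at the point in the trial when fewest men can still be reached. The team may learn of a physician dose from a pop-up, lose the man some months later, and hold no release with which to confirm it.

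Verified initiation and completion are primary outcomes. If some true doses can be confirmed only in men who stay in contact, uptake may be understated. If contact at month 9 differs between arms, the error also differs between arms. That is possible here, because the two arms receive different content and t2p trains men to talk with their doctor, but its direction cannot be known in advance.

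**Working it through.** **Inputs from the documents.** Initiation 18-21% in t2p and 6-8% in control, two-sided alpha 0.05, 192 per arm for the power statement, 230 per arm enrolled, attrition 5-20% (all section 11.0).

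**Input assumed.** s, the share of first doses visible only in a chart. The documents give no figure; 20-40% is used.

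**Step 1: the plan's own figure.** Power = Φ[(|p1 − p2| − 1.96·se0)/se1], where se0 = √[2·p̄(1 − p̄)/n] and se1 = √[(p1(1 − p1) + p2(1 − p2))/n]. For the hardest stated scenario, 18% versus 8% with n = 192: p̄ = 0.13, se0 = 0.0343, se1 = 0.0339, power = 83.3%. The other corners give 95.4% (21 v 8), 95.4% (18 v 6) and 99.2% (21 v 6). The claim of more than 80% reproduces. With n = 230 and no lost doses, 18% versus 8% gives 89.3%.

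**Step 2: share of initiations at risk.** Share = u × s, where u is the share of men out of contact. This takes vaccinated men to be lost at the same rate as others, wherever they were vaccinated.

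- Low: 0.05 × 0.20 = 0.01
- High: 0.20 × 0.40 = 0.08

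This is a ceiling for this mechanism, because a man lost before reporting any dose would not enter the chart route whenever the release was requested.

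**Step 3: in men.** Expected initiators are 230 × 0.18 = 41.4 in t2p and 230 × 0.08 = 18.4 in control.

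- t2p: 41.4 × 0.01 = 0.4 to 41.4 × 0.08 = 3.3
- control: 18.4 × 0.01 = 0.2 to 18.4 × 0.08 = 1.5

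**Step 4: power, if unverified doses were counted as no dose.** This counting rule is a working assumption, not the plan's. Both rates are multiplied by (1 − u·s), n = 230 per arm, true rates 18% versus 8%.

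| u | s | observed rates | power |
|---|---|---|---|
| 5% | 20% | 17.8% v 7.9% | 88.9% |
| 5% | 40% | 17.6% v 7.8% | 88.6% |
| 20% | 20% | 17.3% v 7.7% | 87.8% |
| 20% | 40% | 16.6% v 7.4% | 86.2% |

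Even at s = 100%, with 20% lost in both arms, power is 80.5%.

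**Step 5: unequal loss, as an illustration.** The documents give no attrition by arm. Take the two ends of the stated range, one per arm, with s = 40% and a true difference of 10 points.

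- 20% lost in t2p, 5% in control: 0.18 × 0.92 = 16.56% v 0.08 × 0.98 = 7.84%; difference 8.7 points, power 81.7%.
- 5% lost in t2p, 20% in control: 0.18 × 0.98 = 17.64% v 0.08 × 0.92 = 7.36%; difference 10.3 points, power 91.8%.

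At the extreme of s = 100%, the first split gives 64.5% power and the second 94.8%.

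Completion was not computed, because the plan states no completion rates.

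**The case against.** Several stronger readings are tempting, and the documents do not support them.

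- *Every dose in an unreachable man is lost.* The end-of-trial registry check covers all RCT participants and does not depend on contact. Only doses absent from I-CARE are exposed.
- *Unverified doses are scored as none.* No section says so. The plan is silent on how an unverified self-report counts and on how missing status is classed under intent-to-treat.
- *Only the 9-month survey triggers the chart check.* Sections 9.0 and 25.0 refer to men who report doses over the whole trial, so a pop-up report fits. Section 8.0 sets the chart route beside the 9-month assessment, so the wording is at most ambiguous.
- *The request comes after the last payment.* The text does not order the two. Section 9.0 also lets hard-to-reach men complete a short survey by phone with the coordinator, and one contact could serve both purposes.
- *The loss is much larger because reachable men will not sign.* No refusal rate is given, and men can refuse at baseline too.

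It can also be said that asking all 460 men for chart access burdens many for the sake of a few, in a study whose named greatest risk is loss of confidentiality, and that a chart request about HPV vaccination could hint at the trial's target to a control arm meant to be blinded. Both are fair, though the baseline vaccination questions already hint at the target. They favour asking when a man first reports a dose. The consent forms and supporting documents are not in the reviewed text, so an earlier release there cannot be ruled out; the two sections that give a time both place the request at the end.

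What remains is the narrow gap: a reported, physician-given, off-registry dose in a man who is then lost cannot be chart-verified.

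**Conclusion.** The concern holds in this limited form and is worth a cheap correction. With the stated 5-20% attrition and an assumed 20-40% of first doses visible only in charts, at most 1-8% of initiations are at risk. With equal loss in the arms, power for initiation stays at about 86-89%, against 89.3% with none lost, so the power claim is not undermined. What matters is that uptake may be understated in a pilot meant to inform a larger trial, and that the comparison may be biased in either direction if contact is lost unequally. A reader might infer that the plan discards these doses; it does not say that, and the rates and power above rest on treating them as no dose.

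**What to change.** Change the release wording in sections 9.0 and 25.0, and align section 8.0, so that the form is requested before contact can be lost. Either of two routes would do:

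1. an optional release after the baseline consent, not a condition of entry, covering HPV doses to the end of follow-up; or
2. a request as soon as a man first reports a physician-given dose in any survey or pop-up.

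Keep the end-of-trial request as a back-up for men who have not signed. State that any self-report during the 9 months triggers the chart check when the dose is not in I-CARE, whether or not the 9-month survey is completed.

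The cost is IRB and form wording, some refusals and a small privacy burden, which is wider under route 1 because every man is asked. The chart request itself is still made by the same coordinator. Section 29.0 obtains consent by an online click whereas the release must be signed, so the team should confirm what form of signature providers and the IRB will accept. The change does not recover doses in men lost before reporting any dose. Nor does it settle how an unverified self-report is counted, which needs its own sentence in section 11.0.

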10.0 Data and Specimen Banking

Specimen Banking

No specimens will be banked for future use.

Data Banking

The research team agrees to develop a transportable de-identified database, codebook, and mechanism by which data could be shared with other investigators upon approval of the CO-PIs. Data will be stored in the secure Feinberg School of Medicine managed storage system.

Interested investigators will be asked to complete a standardized request form stating the specific aims of the analysis, the analytic plans, resources the requestors have to carry out the project, the proposed timeline, and distribution goals (manuscripts and/or grant application). The CO-PIs will review these requests to determine whether the proposed analyses constitute an innovative and significant exploration of the data, whether the proposed team has sufficient resources to undertake the request, how data will be protected/managed, and whether there are sufficient resources to honor the request. If any of these issues are problematic, the CO-PIs will attempt to negotiate a fair resolution with the interested parties and/or with NIH program staff. The CO-PIs will keep a record of all individuals/research teams who receive a copy of the data.

11.0 Data and Specimen Management

Analysis Strategy

Intervention feasibility will be computed as outlined above and summarized in a CONSORT map. Acceptability of the intervention will be assessed with descriptive statistics for the closed-ended items and with the same qualitative approach used for the online FG data for the open-ended items. Intervention efficacy will be assessed using an intent-to-treat approach. T-tests and chi-square analyses will be used to compare baseline characteristics of participants in the treatment vs. control condition. Separate chi-square analyses will be conducted for HPV vaccine initiation (receipt of ≥ 1 dose) and completion (receipt of 3 doses) to assess effects of treatment. Secondary analyses will examine potential differences in IMB constructs at the end of Phase 1 by treatment arm and assess whether they mediate effects of t2p on vaccine uptake. Following [name],³⁴ we will also conduct a detailed analysis of barriers to vaccine uptake among participants who did not get vaccinated over the course of the study to inform additional modifications for the large-scale trial.

Power Analysis

Based on previous studies,^{14, 41, 43, 54} we hypothesize that 18-21% of treatment arm participants will receive their 1st dose of HPV vaccine, compared to 6-8% of control arm participants. The comparison of outcomes between arms, with two-sided alpha = 0.05, will have $> 80\%$ power for all scenarios with N=192 per condition. Based on previous

PROTOCOL TITLE: txt2protect

studies with similar samples (G2G, Keep It Up! [KIU!])^{38, 49} and retention rates as high as 85-95% with follow-ups as long as one year, we anticipate an attrition rate of 5-20%. Using the most conservative estimate (20%) we will enroll 230 participants per arm to account for attrition.

Steps to Maintain Data Security and Confidentiality

Participant privacy and data will be carefully protected. Online surveys will be conducted online using a secure web-based application (REDCap).

To maintain privacy in the online focus groups, all participants will be asked to use pseudonyms rather than their real names, and to refrain from mentioning others by name. This will help to ensure openness. If any personal information is inadvertently disclosed, names or other identifying information will be redacted from the focus group transcripts.

Each participant will be given a unique identifier in the data set which will be stripped of all personal information to protect confidentiality. Data sets used for analysis will contain participant identification numbers but neither names nor other identifying information such as home address. Identification information will be retained by the PI for the duration of the study and stored separately from the responses provided by subjects.

Collaborators will receive data stripped of personal identifiers (de-identified data). To ensure complete confidentiality, access to the “key” linking personal identifiers to usernames and passwords will be restricted to the CO-PIs. Reports will not identify individual participants. Drs. [name] and [name] will oversee the data storage and reporting procedures. De-identified data will be stored into perpetuity. The “key” linking personally identifiable information to the participant’s ID in the data set will be destroyed at the end of the study. Reports will only use aggregated data. All study staff will be trained in security and confidentiality procedures before receiving access to any participant data.

Data will be stored on a dedicated secure server at the Feinberg School of Medicine. All data will be transmitted securely by connecting to the SFTP server using the encrypted SSH protocol. Users initiate that connection using a client application like Filezilla. The connection uses a non-standard port to further obscure the connection. A username and strong password will be assigned to each user and each username is unique to an individual. User accounts on the server can only access data folders that have been assigned to them. The CO-PIs are responsible for telling the system administer if there are new users or users that should be deleted. The CO-PIs are responsible for all additions, edits, or deletion of data during the study.

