1.0 Objectives

Objectives and Aims

The objective of this project is to develop and pilot test a text messaging intervention to increase human papillomavirus (HPV) vaccination in young adult men who self-identify as gay, bisexual, or queer (which for the sake of brevity, will be referred to as MSM throughout this application, although some men will be sexually inexperienced).

Specific Aim 1: Develop, iteratively refine, and pre-test messages using a 5-step formative research procedure. To achieve this aim we will use a well-established formative approach for designing targeted health interventions. The procedure consists of 5 steps: 1) conduct online focus groups, an online survey, and in-depth interviews to inform message content, 2) draft initial messages based on focus group findings and pilot data, 3) refine message content and assess acceptability using content advisory teams, 4) conduct internal alpha testing to ensure software functionality, and 5) beta test the protocol. Intended users of the program (i.e., MSM aged 18-26 years old from the Chicago metro area) will be recruited to assist with this process.

Specific Aim 2: Test the feasibility, acceptability, and preliminary efficacy of the txt2protect (t2p) text messaging intervention in a pilot randomized controlled trial (RCT). To achieve this aim, 460 unvaccinated MSM (ages 18-26) who live in the Chicago metro area will be randomly assigned to the treatment (t2p) or control condition. The treatment condition will receive a culturally appropriate text messaging-based HPV vaccination intervention based on the IMB model, whereas the control condition will receive a text messaging-based sexual health intervention that includes basic facts about HPV vaccination readily accessible online. Primary outcome measures include intervention feasibility (recruitment and retention in the trial), acceptability (satisfaction with the intervention), and preliminary efficacy as determined by initiation (receipt of the first dose) and completion of the 3-dose HPV vaccine series at the end of the 9-month trial. Vaccination status will be verified by participants' medical records and the Illinois Immunization Registry.

Hypotheses

Specific Aim 2: Participants in the t2p condition (vs. control) will report greater acceptability of the intervention and will be significantly more likely to initiate and complete the 3-dose HPV vaccine series by the end of the trial.

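### Section 1.0 predicts greater acceptability with t2p than with control, but the plan commits to no analysis that compares the arms on acceptability

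*Combined protocol and SAP*

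**What the plan says.** Section 1.0, Specific Aim 2, places acceptability among the primary outcomes: "Primary outcome measures include intervention feasibility (recruitment and retention in the trial), acceptability (satisfaction with the intervention". The hypothesis for that aim is directional and compares the arms: "Participants in the t2p condition (vs. control) will report greater acceptability of the intervention". Its second half predicts that t2p participants will be significantly more likely to start and finish the vaccine series.

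Section 8.0 sets the timing, "Intervention acceptability will be assessed at the end of Phases 1 and 2", and the criterion, "Average scores ≥ 4 will be used to indicate an acceptable intervention". The one closed-ended item shown as an example is scored 1 to 5. The criterion names no arm, but Aim 2 is worded as "Test the feasibility, acceptability, and preliminary efficacy of the txt2protect (t2p) text messaging intervention", so t2p is evidently its target.

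Section 11.0, Analysis Strategy, says "Acceptability of the intervention will be assessed with descriptive statistics for the closed-ended items" and assigns the open-ended items to the qualitative method used for the focus groups. The same paragraph names comparisons by arm elsewhere. Baseline characteristics get t-tests and chi-square tests. For vaccination, "Separate chi-square analyses will be conducted for HPV vaccine initiation", and likewise for completion. For the Information, Motivation and Behavioral Skills (IMB) constructs, "Secondary analyses will examine potential differences in IMB constructs at the end of Phase 1 by treatment arm".

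**The concern.** One sentence in section 1.0 makes two comparative predictions. The vaccination prediction has a named between-arm analysis and the acceptability prediction has none. A set of secondary measures (the IMB constructs) is to be examined by arm, while a primary outcome with a stated direction is not.

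At stake is whether the trial can report on its own hypothesis. A team that followed the plan to the letter could state whether t2p reached an average of 4 and could summarise the item responses. It would have no prespecified estimate of how far t2p differs from control, and no measure of how uncertain that difference is.

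**Working it through.** **1. The plan's own figure.** The only power statement (section 11.0, Power Analysis) concerns receipt of the first dose: above 80% with 192 per arm, two-sided alpha 0.05, 18-21% against 6-8%. For the least favourable pair, 18% against 8%, the pooled rate is 0.13 and

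power = Φ{[0.10 − 1.96·√(2·0.13·0.87/192)] / √[(0.18·0.82 + 0.08·0.92)/192]} = Φ{(0.10 − 0.0673)/0.0339} = Φ(0.964) = 83%.

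The other three pairs give 95.4%, 95.4% and 99.2%, so the statement reproduces. It covers vaccination only. The plan gives no precision or power for acceptability, and the power section's reference to comparing outcomes between arms follows first-dose rates alone.

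**2. Hypothesis against planned analysis.**

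| Comparative claim or measure | Between-arm analysis named in section 11.0 |
|---|---|
| Vaccine initiation and completion (section 1.0 hypothesis) | Chi-square tests |
| IMB constructs (secondary) | Differences by arm, and mediation |
| Baseline characteristics | t-tests and chi-square tests |
| Acceptability (section 1.0 hypothesis, primary outcome) | None |

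**3. Can the benchmark stand in for a comparison?** No, as a matter of logic. Take, for illustration only, a t2p average of 4.2. The benchmark is met whether the control average is 4.0 (hypothesis supported), 4.2 (no difference) or 4.4 (direction reversed). Applying the benchmark to both arms would not rescue it. Both arms could pass, or both fail, whatever the difference between them. One arm just above 4 and the other just below would differ trivially.

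**4. What a between-arm estimate would deliver.** Inputs: 230 enrolled per arm, 1:1 allocation and 5-20% anticipated attrition (sections 9.0 and 11.0). Retained per arm: 230 × 0.80 = 184 and 230 × 0.95 = 218.5, taken as 218. The planned 192 and the full 230 are also shown. With equal arms and a common SD,

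95% CI half-width = t(0.975, 2n − 2) × √(2/n), in SD units.

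The documents give no SD for the scale. The last column assumes an SD between 0.6 and 1.2 points.

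| n per arm | Half-width (SD units) | In points, SD 0.6 to 1.2 (assumed) |
|---|---|---|
| 184 | 0.205 | 0.12 to 0.25 |
| 192 | 0.201 | 0.12 to 0.24 |
| 218 | 0.188 | 0.11 to 0.23 |
| 230 | 0.183 | 0.11 to 0.22 |

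**5. Why these are best cases.** They assume that every retained participant in both arms contributes a score. Section 9.0 lets participants skip questions. It also offers hard-to-reach participants a short Phase 2 survey centred on the primary outcomes, without saying whether the acceptability scale is included. If scores are lost in either way, the Phase 2 interval will be wider.

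**6. Does the control arm have the data?** Section 9.0 (Sources of Materials) gives one assessment schedule for everyone in the pilot RCT, which implies that control participants complete the scale. No section says so. The draft RCT surveys (Appendix 5) would settle it but are not reproduced in the document.

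**The case against.** The strongest reply is that this is a pilot whose only stated criterion for acceptability is the benchmark, and the descriptive plan serves that criterion. In a two-arm trial, descriptive statistics would naturally be tabulated by arm. With means, SDs and numbers by arm, anyone could compute the difference and its interval. This is a fair reading and it limits the point. It remains a reading and not a commitment: section 11.0 names the arms for other measures and does not do so here.

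A reader might infer more than the documents support:

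- *That a promised significance test is missing.* In the section 1.0 hypothesis, the word significantly attaches to vaccination only. What is missing is a between-arm estimate with its uncertainty.
- *That comparison by arm is ruled out.* Nothing excludes it; the plan is silent.
- *That the benchmark is too easy to meet.* How often it is met depends on a true mean and an SD that the documents do not give, so no such claim can be made.
- *That failing to name Phase 1 or Phase 2 as the main assessment is an error in itself.* Both are specified, and reporting both is coherent for an exploratory estimate.

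It is also fair to object that the proposed interval depends on control participants completing the scale. That stands, and it makes the fix conditional.

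**Conclusion.** The mismatch holds on the text. The protocol states a directional between-arm hypothesis on a primary outcome, and sections 8.0 and 11.0 commit to nothing that answers it.

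Its consequence is minor to moderate. No decision rule turns on the acceptability difference, and the vaccination analyses do not depend on it. It would be wrong to infer that the trial's efficacy conclusions are at risk. The point goes a little beyond missing detail, because a difference with an interval lets the trial address its own prediction at almost no cost.

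The textual finding rests on no numerical assumption. The precision of about 0.18 to 0.21 SD assumes equal arms, a common SD, retention within the plan's own range and complete scale data in both arms. The conversion to points rests on the assumed SDs.

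**What to change.** First confirm that control participants complete the same acceptability scale, and say so in section 8.0 or 9.0.

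If they do, add to section 11.0 wording such as: *The mean closed-ended acceptability score will be reported by arm at the end of Phase 1 and at the end of Phase 2, with the number of participants contributing, the between-arm mean difference and its 95% CI at each time point. This comparison is exploratory; no confirmatory test is planned.* Keep the benchmark of at least 4 as a separate criterion and state that it applies to t2p.

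If they do not, reword the acceptability hypothesis in section 1.0 as non-comparative, so that the benchmark and the descriptive plan match it.

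The cost is two or three sentences in section 11.0, or one reworded hypothesis, and slightly more analysis work. No new data are needed if the control arm already completes the scale.
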